Demographics, Smoking history, Cigarette characteristics, and Nicotine Dependence (FTND): Standard questionnaires will be administered to assess participants': demographics, age at smoking initiation, current smoking rate, previous quit attempts, and own cigarette brand characteristic information (Cigarette Brand Form). Cigarette characteristics will include: length (king/regular, 100, 120, other), filter status (filtered vs. nonfiltered), pack type (soft vs. hard), tar and nicotine yield, and brand name/variety. We will also administer the Fagerstrom Test for Cigarette Dependence (FTCD),¹⁶ a 6-item, self-report measure of nicotine dependence. The FTCD scale has satisfactory internal consistency (Cronbach's alpha = .64) and high test-retest reliability ($r = .88$).

Alcohol use: We will administer an alcohol use questionnaire to assess alcohol consumption over the past 7 days.

Primary Outcome Measures:

Product perceptions will be assessed using multiple questionnaires:

- a. **Risk beliefs:** A previously validated 8-item scale¹⁷⁻¹⁹ will be administered at the beginning of the study session (regarding their own brand) and after each cigarette smoked in the laboratory (regarding these cigarettes), while physically viewing the pack, to assess participant's perceptions of harms from using the product. We will examine both a summed composite score and individual items rated on a 5-point Likert scale (1 = "definitely untrue", 5 = "definitely true") that evaluate participants' preferred brand and the cigarettes they smoked on the following beliefs: a) "lower in nicotine", b) "lower in tar", c) "less addictive", d) "less likely to cause cancer", e) "has fewer chemicals", f) "is healthier", g) "makes smoking safer", h) "helps people quit smoking."
- b. **Perceived health risks:** At the beginning of the study session and after using each laboratory cigarette, participants will complete a 13-item measure²⁰ asking them to indicate on a 7-point Likert scale (1 = "very low risk", 7 = "very high risk") their risk of developing 11 health conditions (i.e., lung cancer, heart disease, stroke, high blood pressure, diabetes, asthma, liver disease, emphysema, respiratory infections, other cancers, and addiction) based on regular use of their preferred brand and each cigarette they sampled. Two additional items will ask about overall risks of using the cigarettes for themselves and for others.

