- c. **Subjective ratings:** Subjective ratings will be measured after each cigarette smoked during in-person visits using 14 individual items assessing various cigarette characteristics (e.g., strength) used by the tobacco industry and our laboratory.^{17,21-23} Items are rated on a 100 mm visual analog scale with item-specific anchors (e.g., strength: 0 = "very weak," 100 = "very strong"); lower scores indicate less favorable ratings.

Product use

- a. **Video-scored smoking behavior:** Participants' puffing behavior will be collected using a validated procedure to score video recorded smoking sessions.²⁴ We previously demonstrated that video-observed puffing behavior measures are interchangeable with those collected by electronic topography devices. We

will quantify puffing behavior for this study using the same procedures to obtain estimated number of puffs taken, the duration of each puff, and interpuff interval (time between puffs).

b. Cigarette purchase task: Behavioral economic indices of demand will be measured using a hypothetical purchase task. Participants will be asked how many cigarettes (preferred brand and study-supplied) they would purchase and consume in the next 30 days across a range of prices, from free up to high amounts at which purchase/consumption is expected to drop off.

Exposure:

a. Carbon monoxide (CO): CO will be measured in parts per million (ppm) using the Vitalograph BreathCO carbon monoxide monitor (Lenexa, KS) at the onset of the laboratory visit, as well as before and after each cigarette smoked. CO at the onset of each visit represents daily exposure, while CO boost – the change in CO values resulting from smoking a cigarette – crudely estimates smoke exposure due to smoking an individual cigarette.

Secondary Outcome Measures and Covariates:

Craving: Craving will be assessed using at the beginning of the session using the Questionnaire on Smoking Urges (QSU). A “Right Now” frame of reference to determine factor subscales and a summary score from a 32-item Likert-format self-report instrument will be used to assess smoking urges and cravings over the course of the study. Questionnaire items are separated into four areas: 1) desire to smoke, 2) anticipation of immediate positive outcome from smoking, 3) anticipation of immediate relief from nicotine withdrawal or relief from negative affect, and 4) intentions to smoke.

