4. FTCD
5. Contemplation ladder
6. Craving (QSU)
7. Withdrawal (WSCW)
8. Risk beliefs (own brand)
9. Perceived health risks (own brand)
10. Purchase task (own brand)
11. Brand appeal (own brand)
12. Pre-cigarette CO reading(s)

The following measures will be completed by participants after each cigarette smoked during the session:

1. Post-cigarette CO reading(s)
2. Subjective ratings
3. Risk perceptions
4. Perceived health risks
5. Attitudes and intentions
6. Purchase task
7. Brand appeal

The following measures will be completed by participants at the conclusion of the session:

1. Final cigarette rating scale
2. NAS & charcoal knowledge

5. Data Management:

A data management system (DMS) developed by the CIRNA Data Management Team will facilitate the operational facets of this study, including determining initial eligibility and producing lists of subjects for telephone contacts for scheduling, and data entry. The DMS uses the relational database product Microsoft Access as the primary software platform for data entry and validation, storage, retrieval, modification, and security. The DMS ensures data integrity through range and validity checks during the data entry process. Daily backups are performed to protect data from accidental destruction or corruption.

The CIRNA Data Manager will work closely with the PI, [name], to develop an understanding of the data collection, storage, and quality assessment needs for the study (e.g., design and development of data collection forms and any additional administrative CRFs) to ensure that standardized, uniform data collection and management procedures throughout the duration of study enrollment. The Data Manager will work closely with the PI and senior personnel to design, develop, and test an appropriate database structure to support the requirements of the DMS and to promote data security and integrity. Electronic audit trails of changes to database contents are incorporated into the design and will capture and record those changes automatically. In addition to the study database where actual results will be maintained, a development database will be created. The development database is a working environment that facilitates the development, testing, troubleshooting, enhancement, and training for the DMS without adversely affecting the integrity of the collected project data.

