The Data Manager will develop a module to assist study staff in participant recruitment and retention tracking. This module will accept and store contact information for potential subjects and will include data items to indicate the completion status of significant events. The tracking module will include information about contact and visit schedules to assist in preparing communications to potential and active participants concerning scheduled events. The module will also allow for incentive-related inventory management.

6. Subject Follow-up:

Not applicable. We will not follow up with participants after they complete the single study visit.

STUDY PROCEDURES:

1. Detailed Description:

Telephone eligibility interview (duration: ~0.5 hours): Trained personnel will determine participants' initial eligibility during a structured telephone interview. Those who meet eligibility criteria will be scheduled for the in-person visit.

Laboratory visit (duration: ~2.5 hours): The single study visit will occur at the Center for Interdisciplinary Research on Nicotine Addiction (CIRNA). Upon entering the CIRNA for this session, participants will complete the following:

1. Confirm the accuracy of information (i.e. name, address, phone number, email [if applicable], date of birth, age, ethnicity, race, and cigarette brand type) provided during the initial Telephone Eligibility Screening.
 - a. Participants must bring in a pack of their own preferred brand of cigarettes to verify their cigarette brand type.
 - i. If a participant forgets to bring a pack of their preferred brand of cigarettes, their session may be rescheduled to a later date or the participant may be deemed ineligible at the discretion of the PI.
2. Hear a study description where all study procedures will be reviewed.
 - a. The combined informed consent and HIPAA will be read verbatim. All questions will be answered as appropriate after which the combined informed consent and HIPAA form will be completed (signed and dated) by the participant and a member of the research staff.
3. Perform a CO breath assessment and self-report smoking behavior over the past 24 hours to control for prior tobacco exposure.
 - a. Participants with a CO reading < 5 ppm will be ineligible.
4. Height and weight measurements.
5. Complete a Medical History Form with a member of the research staff to review for applicable contraindications previously listed under Key Inclusion/Exclusion Criteria.

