To inform subjects prospectively of the use of deception/incomplete disclosure, we have included the following suggested consent language on our consent document (see Informed Consent document): "In some research studies, the investigators cannot tell you exactly what the study is about before you participate in the study. We will describe the tasks in the study in a general way, but we can't explain the real purpose of the study until after you complete these tasks. When you are done, we will explain why we are doing this study, what we are looking at, and any other information you should know about this study. You will also be able to ask any questions you might have about the study's purpose and the tasks you did. Though we may not be able to explain the real purposes of the study until after you complete the tasks, there are no additional risks to those that have been described in this consent form."

Upon completing the full survey, participants will be debriefed of the true study purpose. They will be told that we were specifically interested in understanding the effects of cigarette packaging and filter type on their perceptions and use of the product, and that we were initially vague about our procedures to avoiding biasing their responses toward the study manipulations.

5. Statistical Analysis:

Analytic plan. Main and interaction effects of filter and pack type will be analyzed using univariate analysis of variance (ANOVA) models in SPSS IBM Statistics v26. Primary outcomes are continuous, and based on previous work^{17,21,22} are expected to meet normality assumptions. Analyses will first include only main and interaction effects, then will include as covariates any baseline variables demonstrating a bivariate association of $p < 0.25$ with a given outcome measure.

Power analysis and sample size. A priori power analyses were conducted for primary aims using G*Power v3.1.9.2. These analyses determined that a target sample size of 40 will be adequate to detect a significant small-to-medium effect (partial $\eta^2 = .05$, $\alpha = 0.05$, within-subject correlation = 0.5) of the 2 x 2 between-within subject interaction on a univariate outcome with 80% power.

RISK/BENEFIT ASSESSMENT:

1. Risks:

The potential risks to participants, and their likelihood and seriousness, are minimal and described below. Participants can choose, as an alternative, to not enroll in this study.

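### Each outcome is analysed unadjusted and again with covariates screened at p < 0.25, and neither model is named primary; the pack effect (Aim 2) can turn on that choice

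*Combined protocol and SAP*

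**What the plan says.** Under STUDY PROCEDURES, 5. Statistical Analysis, the sequence is "Analyses will first include only main and interaction effects", and the models "then will include as covariates any baseline variables demonstrating a bivariate association of" p < 0.25 with the outcome in question. The section does not say which model carries the conclusion, what is reported if they differ, which baseline variables are candidates, or how many may enter.

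Elsewhere the protocol points to covariates without fixing a set:

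- The laboratory visit, step 3, has participants "Perform a CO breath assessment and self-report smoking behavior over the past 24 hours to control for prior tobacco exposure".
- METHODS, 1. Study Instruments has a heading for secondary outcomes and covariates, and describes the contemplation ladder as a possible covariate.
- Baseline collection is wide. The smoking-history and brand forms alone cover "age at smoking initiation, current smoking rate, previous quit attempts, and own cigarette brand characteristic information".

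The screen is repeated for every outcome, and there are many. For risk beliefs: "We will examine both a summed composite score and individual items rated on a 5-point Likert scale". Subjective ratings are taken "using 14 individual items assessing various cigarette characteristics". Video scoring yields "estimated number of puffs taken, the duration of each puff, and interpuff interval". Perceived health risks, the purchase task and CO boost are also primary.

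**The concern.** Two results per outcome with no stated precedence leave open which one is the finding. The second model is also chosen from the outcome data, so its covariates can differ between items of one scale. It can omit session-onset CO or past-24-hour smoking, which the protocol says are collected to control for prior exposure. With 40 participants and a long baseline battery, the screen can admit many irrelevant variables.

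Pack colour is assigned between participants, so the pack effect is the comparison that participant-level covariates alter. At stake is whether a claim about packaging depends on an unstated choice of model, and whether precision is lost to noise covariates when a good baseline measure is already collected.

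**Working it through.** **1. The plan's own figure.** Inputs from 5. Statistical Analysis: partial eta-squared 0.05, N = 40, m = 2 measurements, within-subject correlation 0.5, alpha 0.05. f² = 0.05/0.95 = 0.0526. For the interaction, lambda = f² × N × m/(1 − 0.5) = 0.0526 × 40 × 2/0.5 = 8.42 on 1 and 38 df. Power is 0.807, so the stated 80% reproduces.

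**2. The same effect size applied to pack.** lambda = f² × N × m/(1 + 0.5) = 0.0526 × 40 × 2/1.5 = 2.81, giving power of about 37%. As a standardised difference in participant means, d = √(4 × 2.81/40) = 0.53. The SD of a mean of two cigarettes is √0.75 = 0.866 of the single-cigarette SD, so this is 0.53 × 0.866 = 0.46 SD per cigarette. Applying this effect to pack is an assumption; the plan gives it only for the interaction.

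**3. Counts.** Primary outcomes: 9 risk-belief scores + 14 subjective items + 3 puffing measures + at least 1 each for health risks, purchase task and CO boost = at least 29. The plan gives no candidate count. My tally, counting each scale once, is about 25:

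- height and weight (2)
- own-cigarette length, filter status, pack type, tar and nicotine yield (5)
- age at initiation, smoking rate, quit attempts, dependence score and alcohol (5)
- craving, withdrawal and contemplation ladder (3)
- four own-brand scales (4)
- onset CO, past-24-hour smoking, age, ethnicity and race (5)
- sex (1)

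Results are shown for 5 to 25 candidates.

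**4. The screen.** With 40 participants, p < 0.25 means |r| > 0.186. If no candidate is related to the outcome, 25 × 0.25 = 6.25 enter on average. A control variable with true r = 0.2 fails the screen in 45% of trials; with r = 0.3, in 22%.

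**5. Simulated pack test.** 8,000 trials per setting, 20 per pack (the allocation ratio is not stated), participant means, d = 0.53. The own-brand score has r = 0.5 with the outcome; the other candidates are noise. Ranges cover candidate inter-correlations of 0, 0.3 and 0.5.

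| Candidates | Screened power | Models disagree |
|---|---|---|
| 5 | 43.5-44.5% | 18-19% |
| 10 | 41.3-41.9% | 20% |
| 20 | 35.0-37.8% | 21-22% |
| 25 | 31.6-35.2% | 23-25% |

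For comparison, own-brand only has 45.4-47.1% power and the unadjusted model 36.9-38.4%. With 25 candidates the screen admits on average 7.0, 11.2 or 16.5 covariates as the inter-correlation rises.

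- Own-brand r = 0.3, 25 candidates: screened 26.9-30.8%, own-brand only 39.1-39.8%, unadjusted 36.5-37.5%; disagreement 17.5-21.3%.
- No prognostic candidate, uncorrelated: disagreement 8%, 12%, 19% and 20% with 5, 10, 20 and 25 candidates.
- Two further independent predictors at r = 0.4: the ranking reverses. Screened power is 63%, 60% and 52% with 5, 10 and 25 candidates, against 45-46% for own-brand only. If all candidates also inter-correlate at 0.3, it is 49%, 47% and 35% against 47-48%.

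**6. No pack effect.** The screened model alone rejects in 4.5-5.7% of trials. The models disagree in about 2-7%. At least one is significant in 6.1-9.1%. Over 29 outcomes that is 29 × 0.061 to 29 × 0.091 = 1.8 to 2.6 expected false pack results, against 29 × 0.05 = 1.45.

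**7. Filter and interaction.** In 200 complete mixed-design data sets with two participant-level covariates entered as main effects, the filter and interaction estimates changed by less than 1e-14, while the pack estimate moved by up to 0.40. With covariate-by-filter terms and 15 candidates, the interaction verdict differed in 2.5-10% of trials and the filter verdict in about 9% (uncentred covariates).

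**The case against.** The wording describes an ordered sequence, and a natural reading is that both models will be reported with the second as a robustness check. Nothing licenses quoting only the favourable one. That is fair, and the type I inflation arises only under such selection. But the robustness reading is not written down, and it would still leave open what is concluded when the two differ.

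The disagreement rates and power gaps rest on quantities the documents do not give: effect size, own-brand correlation, number of candidates and their inter-correlation. This stands. With own-brand r = 0.5 and 5 to 10 candidates, the screened model beats no adjustment (41-45% against 37-38%). Subjective ratings and puffing (14 + 3 = 17 of the 29 outcomes) have no own-brand baseline, so the own-brand gain does not apply to them; nor does it apply to CO boost.

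A prescribed covariate list could itself leave out variables the protocol earmarks. This also stands, so the fix allows onset CO, past-24-hour smoking or the contemplation ladder to be fixed in advance where no own-brand score exists.

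Finally, this is a pilot powered on the interaction. That limits the weight of the point, but does not remove it: packaging is one of three stated aims.

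**Conclusion.** The concern holds in a limited form. The plan specifies two models per outcome and designates neither; that needs no assumption. If a pack effect of d = 0.53 exists, the models disagree on its significance in about 8-25% of outcomes over 5 to 25 candidates (up to 27% in runs where two or three covariates explain 40% of the variance). If none exists, they disagree in about 2-7%. The screen costs power against one pre-specified own-brand covariate when own-brand r is about 0.3-0.5 and the other candidates are mostly noise: about 33% against 46% at r = 0.5 with 25 candidates, and 42-44% with 10 or 5. In these runs it clearly gained only when other strong, independent predictors existed.

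A reader might infer more, and the documents do not support it:

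- **That the screened model is invalid in itself.** It holds about 5% type I error.
- **That all three aims are compromised.** Filter and interaction tests change only if covariate-by-filter terms are fitted or data are incomplete; the plan does not say that such terms will be used.
- **That the models usually disagree.** They do so in a minority of outcomes, and rarely without a pack effect.
- **That the protocol commits to 25 candidates.** That is a tally of what is collected.
- **That screening biases the pack estimate towards zero.** The direction depends on candidate inter-correlation, which no document gives.

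**What to change.** In 5. Statistical Analysis, name one primary model per outcome, with covariates fixed in advance and entered as main effects only:

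- **Risk beliefs, perceived health risks, purchase task and (secondary) brand appeal:** the own-brand score of the same scale or item.
- **CO boost:** session-onset CO, not the reading before the second cigarette, which follows exposure to the pack and the first cigarette.
- **Subjective ratings and puffing:** the unadjusted model, or a covariate fixed in advance from those the protocol already earmarks (onset CO, past-24-hour smoking or contemplation ladder).

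Report the unadjusted model as a sensitivity analysis wherever an adjusted one is primary, and label any p < 0.25-screened model exploratory.

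The cost is wording; the measures are already collected and N = 40 is unaffected. Each covariate uses about one degree of freedom; if the own-brand score proves useless (r = 0), power falls by about 1 point or less. Precision is lost if an unlisted variable is strongly prognostic: with two such independent predictors at r = 0.4, about 46% against 52% power with 25 candidates, and 45-46% against 63% with 5.

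A one-sentence minimum, making the unadjusted model primary throughout, would settle which result counts. It would leave power near 37% rather than 46% where own-brand r = 0.5, or 39% where r = 0.3.

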Hypothesis 1: Smokers will endorse more favorable product perceptions (i.e., greater subjective ratings and lower perceptions of harm), engage in greater smoking behaviors, and have higher tobacco exposure after smoking the cigarette with the charcoal (vs. non-charcoal) filter.

Aim 2: Assess the acute effects of packaging on product perceptions, use behaviors, and exposure.

Hypothesis 2: Light-colored (vs. black) packaging will be associated with lower perceptions of harm, subjective ratings consistent with lower harm products (e.g., milder taste, weaker strength), greater use behaviors, and greater tobacco exposure.

Aim 3: Examine the interaction of filter type and packaging on product perceptions, use, and exposure.

Hypothesis 3: The combination of light-colored packaging with the charcoal filter (actual product) will have the lowest perceptions of harm relative to other conditions, greatest use behaviors, and greatest tobacco exposure.

BACKGROUND:

The FDA can regulate tobacco products to reduce their negative health impact. Cigarette smoking remains the leading cause of preventable death.⁵ In 2009, the Family Smoking Prevention and Tobacco Control Act (FSPTCA) granted the U.S. Food and Drug Administration (FDA) the authority to regulate the tobacco industry with the intent of protecting the public from tobacco-caused morbidity and mortality.¹ The FSPTCA allows the FDA to regulate the distribution, marketing, and manufacture of tobacco products, provided that rigorous empirical data supports that any regulatory actions taken ultimately benefit public health.¹

The potential and pitfalls of charcoal filters on cigarettes. Within the FDA's regulatory authority is the ability to regulate cigarette design features,¹ such as filter composition and design. There is modest empirical support that using cigarettes with charcoal filters may reduce exposure to some toxic constituents, which could improve health outcomes for users of these products.²⁻⁴ However, there are mixed conclusions about reduced harm resulting from use of charcoal filters in these and other studies, prompting a need for further research on how charcoal filters impact cigarette use and toxicant exposure.

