Tobacco regulatory relevance. By examining the effects of cigarette filter type and pack color on product perceptions, use behaviors, and exposure, this work directly addresses multiple research priorities of the FDA Center for Tobacco Products (CTP), including behavior (how changes in design and packaging affect tobacco use behaviors and perceptions), marketing influences (how marketing impacts abuse liability and product initiation), and toxicity (how product design characteristics impact constituent exposure).

INNOVATION.

This project is innovative for several reasons. To our knowledge, this is the first formal study to address the effect of placing charcoal cigarettes in different packaging contexts, providing the FDA with evidence informing regulatory decisions regarding both cigarette design and marketing. We will study two industry-created packages, primarily defined by their color (black vs. white) and representing extreme ends along a continuum of implicit harm, thus expanding upon previous work using traditional colors (e.g., blue, red) to assess the impact of novel packaging on consumer reactions. By using identical cigarette rods that have different filter compositions, we will also be able to disentangle effects of cigarette design from packaging/other marketing. Finally, smokers will sample the product, simulating actual initial novel product use, rather than respond to product marketing only, building upon previous work on pack color effects using survey methods.¹⁵

CHARACTERISTICS OF THE STUDY POPULATION:

1. Target Population and Accrual:

We aim to enroll, defined as completing the informed consent process, 60 adult smokers from the greater Philadelphia region to obtain 40 eligible study completers (approximately 20 male and 20 female). Recruitment is anticipated to begin in August 2021 and will continue for 2 years. This accrual projection is based on our experience running similar studies with non-treatment seeking smokers requiring multiple visits. As this study consists of a single visit, we do not anticipate significant retention issues, though we do expect some individuals who enroll could be later be deemed ineligible or withdraw their participation.

2. Key Inclusion Criteria:

Eligible subjects will be:

1. Male and female smokers who are between 21 and 60 years of age and self-report smoking at least 5 cigarettes per day for at least the past 12 months.

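### The power statement refers to the primary aims but gives a figure only for the filter-by-pack interaction; that figure does not carry over to the between-subject pack effect (Aim 2), where the same standardised effect would have about 37% power

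*Combined protocol and SAP*

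**What the plan says.** The power paragraph (Study Procedures, Statistical Analysis) opens with "A priori power analyses were conducted for primary aims using G*Power v3.1.9.2". It then concludes that "a target sample size of 40 will be adequate to detect a significant small-to-medium effect" and specifies the effect as that "of the 2 x 2 between-within subject interaction on a univariate outcome with 80% power". The inputs are partial eta-squared .05, alpha 0.05 and "within-subject correlation = 0.5".

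The Objectives list three aims: filter (Aim 1), pack (Aim 2) and their interaction (Aim 3). The second reads "Aim 2: Assess the acute effects of packaging on product perceptions, use behaviors, and exposure" and has its own directional hypothesis. The analytic plan commits to testing all three effects: "Main and interaction effects of filter and pack type will be analyzed using univariate analysis of variance (ANOVA) models".

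Study Design and Method for Assigning Subjects to Groups make filter a within-subject factor and pack a between-subject factor, so each participant sees one pack colour for both cigarettes. The accrual target is "60 adult smokers from the greater Philadelphia region to obtain 40 eligible study completers". No power, sample size or detectable effect is given for the pack effect, and no allocation ratio is stated.

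**The concern.** The opening sentence of the power paragraph is broader than the result that follows. It speaks of the primary aims in the plural, and the result concerns Aim 3 alone. In a mixed design the two kinds of effect are tested against different error terms, so a reader cannot transfer the 80% from the interaction to pack. The positive correlation that makes 40 sufficient for the interaction works against the pack comparison.

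What is at stake is how the Aim 2 result can be interpreted. Without a figure, nothing in the protocol tells the reader how wide the pack estimate will be, or how large a pack difference the study could reliably detect.

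**Working it through.** **Inputs from the protocol.** N = 40 completers; two ratings per participant (m = 2); two pack groups; partial eta-squared .05; alpha 0.05 with an ANOVA F test; correlation rho = 0.5.

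**Assumptions added here.** 20 participants per pack colour. The interaction's effect size and correlation are carried over to pack for illustration, since the protocol sets neither for pack.

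**Effect size.** f² = .05/.95 = .0526, so f = .229.

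**Step 1: the plan's own figure.** With the G*Power default convention for repeated measures, the interaction has

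lambda = f² × N × m / (1 − rho) = .0526 × 40 × 2 / 0.5 = 8.42, on F(1, 38).

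Power is 80.7%, and 40 is the smallest N that reaches 80%. The stated figure reproduces, which identifies the convention used.

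**Step 2: the pack effect on the same inputs.**

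lambda = f² × N × m / (1 + rho) = .0526 × 40 × 2 / 1.5 = 2.81, on F(1, 38).

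Power is 37.2% (36.9% in a simulation of 20,000 trials). The non-centrality is one third of the interaction's, because 0.5/1.5 = 1/3. At this f, 80% power would need N = 114 (80.1%; N = 112 gives 79.4%).

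**Step 3: sensitivity to the correlation at N = 40.**

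| Correlation | Power for pack |
|---|---|
| 0 | 52% |
| 0.3 | 42% |
| 0.5 | 37% |
| 0.8 | 32% |

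**Step 4: what 40 can detect for pack.** Power of 80% on 38 error df needs lambda = 8.27. Then f = √(8.27 × 1.5 / 80) = .394, which is partial eta-squared .134 on the same scale. The pack difference is 2f = 0.79 SD of a single rating. The difference used in step 2 is 2 × .229 = 0.46 SD.

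**Step 5: precision.** The mean of two ratings has variance (1 + 0.5)/2 = 0.75 SD². The standard error of the pack difference is √(0.75 × (1/20 + 1/20)) = √.075 = 0.274 SD. The 95% CI half-width is 2.02 × 0.274 = 0.55 SD.

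**Step 6: gain from a baseline covariate.** If a baseline rating correlates r with the participant's mean rating, lambda becomes 2.81/(1 − r²) on 37 error df.

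| r (assumed) | lambda | Power for pack |
|---|---|---|
| 0.3 | 3.08 | 40% |
| 0.5 | 3.74 | 47% |
| 0.7 | 5.50 | 63% |

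**Step 7: dependence on the effect-size scale.** If partial eta-squared .05 is read on the scale that ANOVA output reports (lambda = f² × N, or f² × (N − 2)), lambda is 2.11 or 2.00. Power is then 28–29% for every effect, including the interaction. This reading does not return the plan's N of 40, but it limits what can safely be written about the other aims.

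**The case against.** **The adequacy claim is limited to the interaction.** This stands. A reader might infer that the protocol promises 80% power for pack, or that its calculation is wrong. The documents support neither: the sentence names the interaction, and its figure reproduces. What remains is that the sentence before it refers to the primary aims, and one of the listed aims has no figure.

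**No planning effect is set for pack.** This also stands, so 37% is a conditional illustration. It would be too strong to say that the trial misses its own planning effect for Aim 2 about 63% of the time. Equal f is not an equal difference in raw terms either: f = .229 is a pack difference of 0.46 SD, but a difference between packs in the filter effect of 4f = 0.92 SD.

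**The contrast between aims depends on the scale.** A reader might infer that Aim 2 alone is weak and that Aims 1 and 3 are secure at 80%. The filter effect does match the interaction at 80.7% on the default scale, but on the ANOVA-output scale all three effects fall to 28–29%.

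**It is a pilot, and nobody has said that a null means no effect.** Correct. A reader might predict that a non-significant pack result will be reported as absence of an effect, but nothing in the documents says so. Pilot status lessens the consequence; it does not supply the missing figure.

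**Covariate adjustment is already planned.** In part. The plan fits unadjusted models first, then adds baseline variables that pass a p < 0.25 screen for each outcome. No covariate is named for Aim 2, and no gain in power is counted.

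**Conclusion.** The point holds as a reporting gap. The interaction's 80% cannot be read across to Aim 2. At the same f on the G*Power default scale, with correlation 0.5 and an assumed 20:20 split, pack has about 37% power (32–42% over correlations 0.8 to 0.3). With 40 completers, 80% power is reached only at a difference of about 0.79 SD of a single rating, and the 95% CI extends about 0.55 SD either side of the estimate.

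The 20:20 assumption matters little: a 16:24 split gives 36%. The transferred effect size matters more, so the detectable difference and the CI half-width are the sturdier figures. They still depend on correlation 0.5 and the 20:20 split, but not on a planning effect for pack.

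**What to change.** 1. In the power paragraph, confine the adequacy sentence to the interaction. Add that the between-subject pack effect (Aim 2) has about 37% power at the same f on the G*Power default scale, with correlation 0.5 and 20 per pack colour, and reaches 80% only at a difference of about 0.8 SD. State that the pack effect will be reported as an estimate with its 95% CI, and that a non-significant result will be treated as inconclusive. Do not add a statement that Aims 1 and 3 have 80% power, because that depends on the effect-size scale.

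2. For the Aim 2 test, pre-specify the matching own-brand baseline rating as the covariate in place of the p < 0.25 screen. The list under Administration of Surveys shows that such ratings are collected for risk beliefs, perceived health risks, the purchase task and brand appeal. Power would rise to about 40%, 47% or 63% if the rating correlates 0.3, 0.5 or 0.7 with the participant's mean; these correlations are assumptions. The step does not apply to subjective ratings, puffing behaviour or CO boost, for which no own-brand counterpart is listed.

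The cost is a less favourable stated figure for Aim 2 and one error degree of freedom (38 to 37). No further participants, visits or measures are needed.
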